#### 11.5.5 Subgroups

The following subgroup populations will be investigated for the main estimand using ITT population:

- Age category (< 65 years and  $\ge 65$  years)
- Gender (male and female).
- Race
- Ethnicity
- Baseline Type 2 Diabetes.

#### 11.5.6 Handling of Missing Data

Every effort will be made to prevent participants early terminating the study and for participants who discontinue study drug, every effort will be made to continue to collect data after

Approved by: [name] No.: SARO.20.001
[name]	Version No.: 4.0

### CONFIDENTIAL Page 66 of 109

discontinuation. Where missing data exist for primary and secondary efficacy endpoints, imputation will occur where specified.

The primary method of imputation for missing data will be MI (Multiple Imputation); the MI procedure of the SAS system will be used to generate sets of data with missing values imputed from observed data. It is expected that the pattern of missing data will be monotonic, as the biopsy will be performed only at screening and at Week 24/EOT visits.

A logistic regression model will be used for the ordinal scores and linear regression will be used for the continuous variable.

The imputed datasets will be analyzed using the methodology described in Section 11.5. The results from the analysis of the multiple imputed datasets will be combined by the MIANALYZE procedure of the SAS system. The number of imputations and the seed to be used, plus any further details required, will be detailed in the SAP.

#### 11.5.7 Sensitivity and Supportive Analyses

The following sensitivity and supportive measures will be conducted for the primary efficacy endpoint:

Estimand	Analysis Set	Modelling and Data Handling Method
Primary and secondary	PPS	Same as primary analysis method. Repeat on primary and secondary estimands with same imputation approach for missing data.

#### 11.6 SECONDARY EFFICACY ENDPOINT AND ANALYSIS

#### 11.6.1 Definitions Applying to All Estimands

Criterion	Description	
Treatment conditions of interest	Saroglitazar Magnesium 4mg vs placebo	8
Population	Participants with NAFLD in PLWH	

### 11.6.2 Details of Each Estimand for the Secondary Efficacy Endpoints Involved in Construction of the Primary Efficacy Endpoint

Approved by: [name] No.: SARO.20.001	
[name]	Version No.: 4.0	

#### CONFIDENTIAL Page 67 of 109

Endpoint	Population Level Summary	Primary Estimand	Secondary Estimand
Reduction of at least 30% in hepatic fat content from baseline following 24 weeks/EOT	Difference between treatments in proportion of participants with reduction of at least 30% in hepatic fat content from baseline following 24 weeks/EOT	Same as primary efficacy endpoint	Same as primary efficacy endpoint

### 11.6.3 Details of Each Estimand for the Secondary Efficacy Endpoints Not Involved in Construction of the Primary Efficacy Endpoint

Endpoint	Population Level Summary	Primary Estimand	Secondary Estimand
LSM, CAP and FAST scores measured by FibroScan®/VCTE Non-invasive markers of fibrosis and steatosis (PRO-C3, FIB-4, APRI, NFS)	Difference between treatments in mean change from baseline in LSM, CAP and FAST scores at Week 24/EOT.  Difference between treatments in mean change from baseline in non-invasive markers of fibrosis and steatosis (PRO-C3, FIB-4, APRI, NFS) at Week 24/EOT.	Premature discontinuation of study treatment for reason other than AE, lack of efficacy (LoE), liver transplant, hepatic decompensation or bariatric intervention  Treatment policy strategy  Premature discontinuation of study treatment for reason of AE, lack of efficacy (LoE), liver transplant, hepatic decompensation or bariatric intervention  Treatment policy strategy  Receipt of prohibited medication at any point up to Week 24  Treatment policy strategy	Not applicable
Liver enzyme parameters (ALT and AST), Lipid parameters (TG, HDL, LDL, VLDL, TC, non-HDL) and insulin resistance and glucose homeostasis markers (HbA1c, FPG)  Body weight, BMI, hip circumference and minimum waist circumference	Difference between treatments in mean change from baseline in liver enzyme parameters (ALT and AST), lipid parameters (TG, HDL, LDL, VLDL, TC, non-HDL) and insulin resistance and glucose homeostasis markers (HbA1c, FPG) at Week 24/EOT.  Difference between treatments in mean change from baseline in body weight, BMI, hip circumference and minimum waist circumference at Week 24/EOT.		

Approved by: [name] No.: SARO.20.001	
[name]	Version No.: 4.0	

#### CONFIDENTIAL Page 68 of 109

Endpoint	Population Level Summary	Primary Estimand	Secondary Estimand
Health related quality of life score measured by SF- 36 Questionnaire	Difference between treatments in mean change from baseline in SF-36 Questionnaire mental (MCS) and physical components scores (PCS) at Week 24/EOT.		

Where the strategies are described as follows in the sequence these strategies will be applied:

#### For the primary estimand:

Composite strategy: Death prior to Week 24 assessment will be handled by imputing using the worst outcome observed for the parameter across either treatment arm.

Treatment policy strategy: available data occurring on or after the ICE will be analyzed as observed. Any missing Week 24 data for the corresponding assessment will not be imputed.

For secondary efficacy endpoints not related to construction of the primary efficacy endpoint, only the primary estimand will be assessed.

#### 11.6.4 Statistical Methods for the Analysis of Secondary Efficacy Endpoints.

The high-level handling approaches for the secondary efficacy endpoints are as follows:

Endpoint	Analysis Set	Modelling Method	Data Handling
Primary Efficacy Endpoints	×	-W	×
Change from baseline in hepatic fat content at week 24/EOT	ITT, PPS	Mixed-effect repeated measures model (MMRM)	As per primary and secondary estimands for the primary efficacy endpoint.
Other Secondary Efficacy End	lpoints		
Proportion of participants with reduction of at least 30% in hepatic fat content from baseline following 24 weeks/EOT	ITT, PPS	Chi-square test as per primary efficacy endpoint analysis.	As per primary and secondary estimands for the primary efficacy endpoint.
Change from baseline in Liver Stiffness Measurement (LSM), Continuous Controlled Attenuation Parameter (CAP), and FibroScan -AST (FAST) score at Week 24/EOT.	ITT	Mixed-effect repeated measures model (MMRM)	As per primary estimand for secondary efficacy endpoints. Missing data will not be imputed.
Change from baseline in non- invasive markers of fibrosis and steatosis (PRO-C3 levels, FIB-4, APRI and NFS) at Week 24/EOT.	ITT	MMRM	As per primary estimand for secondary efficacy endpoints. Missing data will not be imputed.

Approved by: [name] No.: SARO.20.001
[name]	Version No.: 4.0

#### CONFIDENTIAL Page 69 of 109

Endpoint	Analysis Set	Modelling Method	Data Handling
Change from baseline in liver enzyme parameters (ALT and AST) at Week 24/EOT and lipid parameters (TG, HDL, LDL, VLDL, TC, non-HDL) at Week 24/EOT and insulin resistance and glucose homeostasis markers (FPG and HbA1c index) at Week 24/EOT	ITT	MMRM	As per primary estimand for secondary efficacy endpoints. Missing data will not be imputed.
Change from baseline in body weight, BMI, hip circumference and minimum waist circumference at Week 24/EOT.	ITT	MMRM	As per primary estimand for secondary efficacy endpoints. Missing data will not be imputed.
Change from baseline in SF- 36 Questionnaire mental (MCS) and physical components scores (PCS) at Week 24/EOT.	ITT	MMRM	As per primary estimand for secondary efficacy endpoints. Missing data will not be imputed.

#### 11.7 MULTIPLICITY

Not Applicable

#### 11.8 Exploratory Analyses

The exploratory efficacy analysis will be described in the Statistical Analysis Plan.

#### 11.9 SAFETY ANALYSIS

#### 11.9.1 Treatment Exposure

Treatment compliance is calculated as the total number of tablets taken divided by the expected number of tablets to be taken during the study period multiplied by 100. Treatment duration and compliance will be summarized descriptively as a continuous measure. In addition, a categorical summary of compliance will also be presented using the following categories: <80%, 80% to 120%, and >120%. A participant is considered to be compliant, if he/she takes 80% to 120% of the study drug during the study period.

#### 11.9.2 Medical History

Relevant medical history will be tabulated by system organ class and preferred term of the MedDRA dictionary (latest version) presented by treatment group.

Approved by: [name] No.: SARO.20.001
[name]	Version No.: 4.0

#### CONFIDENTIAL Page 70 of 109

#### 11.9.3 Concomitant Therapies

All medications recorded during the study will be coded using the World Health Organization (WHO) Drug Dictionary (latest version). A summary will be provided for the frequency and percent of participants who had concomitant therapy/medications. Summaries will be provided by Anatomical Therapeutic Chemical (ATC) classification level 3 term and Preferred Name.

#### 11.9.4 Safety Parameters

The following safety parameters will be descriptively analyzed:

- Frequency and severity of treatment emergent AEs, serious AEs, and AESIs.
- Changes in vital sign parameters (Systolic BP, diastolic BP, pulse rate, temperature, and respiratory rate)
- Changes in clinical laboratory testing parameters (hematology, clinical chemistry, hormonal profile, and urinalysis)
- Changes in physical examination assessments

AESI includes DILI and weight gain, which would be closely monitored.

AEs/SAEs will be coded using the MedDRA dictionary and presented by system organ class and preferred term. Treatment emergent AEs will be analyzed based on the number and percentage of participants with at least one AE in the category of interest. Additional summaries will be provided by severity and causality. SAEs and AEs leading to discontinuation of study treatment will also be summarized separately. Participant listings of all AEs will be provided. Deaths and other serious or clinically significant non-fatal AEs will be listed separately.

Observed values and changes from baseline will be summarized for the laboratory data and vital signs. Laboratory values will be categorized as low/normal/high according to normal ranges, and shift tables versus baseline will be created to determine treatment-emergent abnormalities. DILI events, as well as important biological consideration events (per Section 7.6) will be categorized based on the relevant laboratory parameters, and summarized by treatment group.

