#### 7.2 INCLUSION CRITERIA

To be eligible to participate in this study, an individual must meet all of the following criteria:

- 1. Adults (≥18 years of age) with documented HIV.
- 2. Documented diagnosis of NAFLD established by imaging (ultrasound, CT scan or MRI) or liver biopsy within 6 months before screening, based on American Association for the Study of Liver Disease [AASLD] criteria
- 3. Hepatic fat fraction ≥8% by MRI-PDFF
- 4. ALT level  $\geq$ 31 U/L in men and  $\geq$ 19 U/L in women at Visit 1 and 2
- 5. HIV-1 RNA <200 copies/mL for ≥6 months on ART (must have screening HIV-1 RNA value and one clinical care value within 6 months prior to screening and up to the randomization that meets the criteria).
- 6. Stable ART regimen for  $\geq 3$  months prior to screening and stable up to the randomization and no active plans to change ART while on study.
- 7. Willingness to participate in the study.

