- 8) Any of the following laboratory values at screening:
  - a. ALT or AST >250 U/L
  - b. Total bilirubin >1.5 mg/dL and direct bilirubin > 0.5 mg/dL (unless due to Gilbert's disease or atazanavir use per the opinion of the site investigator)
  - c. Platelet count <150,000/mm^3
  - d. Estimated glomerular filtration rate (e-GFR) <60 mL/min/1.73m^2 using the chronic kidney disease-epidemiology collaboration (CKD-EPI) equation (Refer Appendix 6 for 'CKD-EPI Calculator')
  - e. International normalized ratio (INR) >1.3.
  - f. Albumin < 3.6 g/dL
- 9) History of malignancy in the past 5 years and/or active neoplasm with the exception of superficial, non-melanoma, skin cancer.
- 10) Unstable cardiovascular disease, including:
  - a) Unstable angina, (i.e., new or worsening symptoms of coronary heart disease) and/or acute myocardial infarction within the 3 months preceding screening
  - b) Acute coronary syndrome or coronary artery intervention within the 3 months preceding screening,
  - c) Heart failure of New York Heart Association (NYHA) class (III-IV) or worsening congestive heart failure within the 6 months preceding screening.
  - d) History of (within 3 months preceding screening) or current unstable cardiac dysrhythmias.
  - e) Uncontrolled hypertension (systolic blood pressure [SBP] >155 mmHg and/or diastolic blood pressure [DBP] >95 mmHg) at screening.
  - f) Stroke or transient ischemic attack within the 6 months preceding screening.

Approved by: [name] No.: SARO.20.001
[name]	Version No.: 4.0

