Normal/near normal baseline a : ALT ≥3x ULN Elevated baseline a : ALT ≥2x baseline or ≥300 U/L (whichever occurs first)	TBL ≥2x ULN Participants with Gilbert's syndrome: Doubling of direct bilirubin or increased INR to >1.5	None	Interrupt study drug. Initiate close monitoring and workup for competing etiologies. Study drug can be restarted only if another etiology is identified and liver enzymes return to baseline.
Normal/near normal baseline a : ALT ≥5x ULN Elevated baseline a : ALT ≥3x baseline or ≥300 U/L (whichever occurs first)	Normal or elevated	Severe fatigue, nausea, vomiting, right upper quadrant pain	Interrupt study drug. Initiate close monitoring and workup for competing etiologies. Study drug can be restarted only if another etiology is identified and liver enzymes return to baseline.

ALP = alkaline phosphatase; ALT = alanine aminotransferase; AST = aspartate aminotransferase; INR = international normalized ratio; TBL = total bilirubin, ULN= upper limit of normal.

Modified from Chalasani N, Regev A. Drug-induced liver injury in participants with pre-existing chronic liver disease in drug development: how to identify and manage? Gastroenterology. 2016;151:1046-1051.

aElevated baseline is defined as ALT  $\geq$ 1.5x ULN. Normal/near normal baseline is defined as ALT < 1.5x ULN. In participants with a sizable stable decrease in ALT (>50% of the baseline value) during treatment, a new baseline, corresponding to the ALT nadir, should be established on an individual basis for subsequent determination of a DILI signal.

bThe actions of close observation, monitoring, and drug interruption often overlap. Occasionally, workup is initiated after drug interruption.

Approved by: [name] No.: SARO.20.001
[name]	Version No.: 4.0

CONFIDENTIAL Page 38 of 109

Table 2. Detection and monitoring of elevated serum alkaline phosphatase

Treatment Emergent Serum Alkaline Phosphatase (ALP) elevations	Serum Total Bilirubin	Action/Follow-up

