#### 12.4 PROCEDURES

#### 12.4.1 Adverse Events

Adverse event reporting will begin after the informed consent has been signed and will continue until end of the study (i.e., the safety follow-up). The National Cancer Institute's CTCAE (Version 5.0 or higher) will be used for reporting and grading AEs when possible.

Approved by: [name] No.: SARO.20.001
[name]	Version No.: 4.0

CONFIDENTIAL Page 78 of 109

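### The low/normal/high laboratory shift table cannot show worsening from an above-range baseline, and moderate rises below the Section 7.6 triggers get no by-arm count

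*Protocol*

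**What the plan says.** Protocol Section 11.9.4 gives the method for laboratory abnormalities: "Laboratory values will be categorized as low/normal/high according to normal ranges, and shift tables versus baseline will be created to determine treatment-emergent abnormalities". The sentence before it adds: "Observed values and changes from baseline will be summarized for the laboratory data and vital signs". The sentence after it says that DILI events and the Section 7.6 biological-consideration events "will be categorized based on the relevant laboratory parameters, and summarized by treatment group".

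Eligibility (Section 7.2, criterion 4) sets an ALT floor of 31 U/L for men and "19 U/L in women at Visit 1 and 2". Section 7.3, criterion 8a, excludes "ALT or AST >250 U/L". AST and ALP have no floor.

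Section 7.6.1.2, Table 1, uses different ALT triggers for raised and unraised baselines. Footnote a states: "Normal/near normal baseline is defined as ALT < 1.5x ULN"; at or above that multiple, baseline counts as elevated. Section 7.6.1.3 likewise has a separate CPK rule for participants with raised CPK at baseline.

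On grading, Section 12.4.1 says that "CTCAE (Version 5.0 or higher) will be used for reporting and grading AEs when possible".

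Protocol Section 11.1 lets the SAP override the protocol where they differ. The SAP covers a terminated study with four randomized participants and plans no formal efficacy analysis. Its Section 13.2 plans individual laboratory listings and summaries of results and change from pre-dose by visit. Its Section 10.4 flags out-of-range values as low or high.

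**The concern.** A three-category shift table works when participants start within range. Here some will start above it: the trial enrols people with fatty liver disease and an ALT floor, and admits ALT and AST up to 250 U/L and HbA1c up to 9.5%. Section 11.4 lists dyslipidaemia and type 2 diabetes as baseline comorbidities. For a participant who starts high, the table looks the same whether the value doubles, rises tenfold or stays put.

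The protocol recognises this problem in Section 7.6, where the ALT and CPK rules change when baseline is raised, but it does not carry the same logic into the table meant to identify treatment-emergent abnormalities. DILI is an adverse event of special interest, so a count of who worsened, by arm, is a display that a safety reader will look for.

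**Working it through.** The plan states no figure on this point, so there is none to reproduce. The check is logical, with small arithmetic.

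**1. The shift table.** Let B be the baseline value and P the worst later value. If B > ULN and P > B, then P > ULN. The cell is high-to-high for every P, whatever P/B is.

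**2. Who can be affected.** The ALT floors are absolute values, and the documents give no ULN. I assume 30 to 55 U/L for illustration. At ULN 30 a man at 31 U/L is already high. At ULN 35 to 55 he is normal, and a rise above ULN would show as a shift. A woman at 19 U/L is normal throughout. The share starting high therefore cannot be calculated from the documents.

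**3. What Table 1 counts (no symptoms, normal bilirubin).** The first trigger is min(3B, 300) if B ≥ 1.5 × ULN, and 5 × ULN if B < 1.5 × ULN. With ULN 40 (assumed), so that 1.5 × ULN = 60:

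| Baseline ALT | First trigger (U/L) | Trigger / baseline |
|---|---|---|
| 50 | 5 × 40 = 200 | 4.0 |
| 60 | min(180, 300) = 180 | 3.0 |
| 100 | min(300, 300) = 300 | 3.0 |
| 150 | min(450, 300) = 300 | 2.0 |
| 250 | min(750, 300) = 300 | 1.2 |

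For baselines from 1 up to 1.5 × ULN, the trigger is between 5/1.5 = 3.3 and 5/1 = 5 times baseline. The row for 100 U/L is the same at every ULN from 30 to 55, because 1.5 × 55 = 82.5 is still below 100. With symptoms, or with total bilirubin at least 2 × ULN, the first trigger falls to 2 × baseline or 300 U/L (3 × ULN for the lower stratum), so the uncounted band is narrower.

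**4. Rises that are high-to-high and reach no Section 7.6 category (no symptoms, normal bilirubin).**
- ALT 100 to 280: 280/100 = 2.8, below 3 times baseline and below 300.
- ALT 50 to 190, ULN 40: 190/50 = 3.8, below 200.
- ALT 100, falling to 45, then 190, ULN 40: the fall is 55%, so footnote a allows 45 as the new baseline. That is below 60, so the trigger becomes 200. Although 190/45 = 4.2, neither 200 nor the 300 from the entry baseline is reached.
- AST 60 to 600, if the AST ULN is below 60: 600/60 = 10. Tables 1 and 2 and Section 7.6.1.3 have no AST trigger. They have none for glucose or triglycerides either.

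**5. What the other displays count.**
- Change from baseline (Section 11.1): n, mean, SD, median, minimum and maximum. One extreme value shows in the maximum; several moderate rises are not counted.
- MMRM (Section 11.6.4): compares mean changes. In the 16-week Phase 2 study described in Section 5.3, mean ALT changed by −44.9% on 4 mg and +2.6% on placebo. A favourable mean of that kind can coexist with individual rises.
- Adverse events (Sections 9.4 and 12.4.1): count only rises that are reported as events.
- SAP: Section 12 defines change as last observed post-dose value minus pre-dose, so a peak that resolves is missed by that measure. The by-visit summaries in Section 13.2 partly offset this. The SAP body names neither a shift table nor a Section 7.6 summary; the content of its table specifications (Appendix-01) is not reproduced.

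**The case against.** The shift table is only one of several displays. Section 11.9.4 itself adds changes from baseline and the DILI categories. ALT, AST, triglycerides and fasting glucose are compared between arms by MMRM. Section 9.4 requires a documented reason if an abnormal test that led to symptoms, further testing or a change in dosing is not reported as an adverse event. A tenfold AST rise would very plausibly be worked up and reported. A blinded hepatic committee adjudicates possible DILI. Table 2 has relative rules for ALP and direct bilirubin, and the 300 U/L limit makes Table 1 sensitive at high baselines. All of this stands, and it makes the gap a narrow one.

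It also rules out stronger readings that a reader might infer:
- *Rises from a high baseline would go unseen.* They would not; several other displays carry them.
- *The between-arm safety comparison is diluted towards no difference.* The comparison does not rest on this descriptive table.
- *The trial selects for raised liver enzymes.* Only ALT has a floor, it may lie inside the laboratory's range, and Table 1 provides for normal or near-normal baselines.
- *Most of the 60 per arm could not register a new high value.* That needs a share above ULN, which the documents do not give.

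What remains is that no display counts, by arm and from measured values, the moderate rises identified above.

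**Conclusion.** The point holds as a limited reporting gap in the protocol's design. The table named for finding treatment-emergent abnormalities cannot show worsening from an above-range baseline, and the displays around it leave moderate rises without a categorical by-arm count. That the table is blind to such rises follows from its three categories and needs no assumption. The ALT 100 to 280 example needs only normal bilirubin, no symptoms and an ALT ULN of 55 U/L or less. The other ALT examples assume ULN 40. How many of the planned 120 participants would be affected is unknown.

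For the analysis that will be reported the effect is small: with four randomized participants, the listings show every value. The MMRM cover also falls away there, because no efficacy analysis will be run.

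**What to change.** In protocol Section 11.9.4, or in any SAP written for the full design:
- For ALT, AST, ALP, CPK, glucose and triglycerides, add to or replace the low/normal/high shift with a shift from baseline to worst post-baseline CTCAE grade, by arm. Where the scale gives no laboratory-based grade for a test, use bands of multiples of baseline.
- For ALT, AST and ALP, tabulate by arm the worst post-baseline multiple of baseline and of ULN.
- Define worst over all post-baseline values, including the unscheduled repeats that Table 1 calls for, and use the baseline defined in SAP Section 10.1.
- Keep low/normal/high for the remaining tests.

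For the four-participant report, adding the worst multiple of baseline and of ULN to the ALT, AST and ALP listings in SAP Section 13.2 is sufficient. The SAP allows revision before final analysis.

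The cost is some wording and a few tables from data already collected, with slightly longer output. No Section 7.6 interruption or stopping rule is altered.
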